All protocol amendments, other than minor administrative changes as defined by the NCCIH Guidance on Changes in Clinical Studies in Active Awards will be submitted in a prospective manner to NCCIH except when necessary to protect the safety, rights, or welfare of subjects. Prior to submission to NCCIH the proposed changes will be reviewed and approved by the Independent Monitor(s). IRB-approval will not be sought until after NCCIH approval of the protocol amendment has been obtained.

M.2.d Confidentiality

Protection of Subject Privacy

Subject confidentiality will be strictly held in trust by the investigators, study staff, and the sponsor(s) and their agents. This confidentiality will extend to cover testing of biological samples and genetic tests, should such data be collected in future protocol amendments, in addition to any study information relating to subjects.

The study protocol, documentation, data, and all other information generated will be held in strict confidence. No information concerning the study or the data will be released to any unauthorized third party without prior written approval of the sponsor.

The study Independent Monitoring Committee (IMC) or other authorized representatives of the sponsor may inspect all study documents and records required to be maintained by the investigator, including but not limited to, medical records (office, clinic, or hospital) for the study subjects. The study site will permit access to such records.

Confidentiality During Adverse Event (AE) Reporting

AE reports and annual summaries will not include subject or group-identifiable material. Each report will only include the identification code.

M.2.e Expected Risks

Expected risks to the subject are as follows:

SECTION P: Documentation

- Rare (<1%) of mild skin irritation due to taping the kinematic markers sensors to the skin. This risk will be minimized by a member of the research team removing the tape with care.
- Rare (<1%) of seizure. Overall estimate is that seizure risk is < 1:1000 (0.1%) and this risk is associated with Repetitive TMS, which will not be conducted in this investigation.

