- Any other unanticipated problem will be reported to the IRB, Independent Safety Monitor(s), and NCCIH within 14 days of the investigator becoming aware of the problem.

All unanticipated problems should be reported to appropriate institutional officials (as required by an institution's written reporting procedures), the supporting agency head (or designee), and OHRP within one month of the IRB's receipt of the report of the problem from the investigator.

Reporting of Pregnancy

Women that are known (via self-report) to be pregnant will be excluded. If a woman becomes pregnant while enrolled, she will not be removed from the study and treatment will be discontinued. Safety follow-ups will be continued for the projected treatment time period. Reporting of participants who become pregnant and are withdrawn from the study will be included in the regular IMC reports as participant drop outs.

M.2.k Halting Rules

Safety findings including, but not limited to, higher than anticipated SAEs, a higher number of a particular SAE than anticipated, and/or increased frequency of AEs.

M.3 Quality Control and Quality Assurance**M.3.a Data Management**

Data will be collected both in hard copy & electronically. All computers in the associated research laboratories are password protected. In order to protect the integrity of the original electronic data files, copies will be made of electronic data files to be used for data manipulation at a later date. Any data file that is amended, cleaned, or updated will be given a new name with the corresponding name of the original file followed by _modified and dated with the month_, day_, and 2-digit year it was modified (i.e. 01_trial_1_modified_4_1_17).

Additionally, data collected in hard copy will be de-identified and transferred to our electronic database as soon as possible. Additionally, hard copy files that have yet to be transferred and originals will be stored in a locked cabinet within the laboratory (i.e. double lock protection). The transfer of data between the PIs for the purpose of monitoring and analysis will only use de-identified data. Further details can be seen in the Confidentiality section below.

M.3.b Data Entry Procedures, Flow, and Checks

1. The programs and data entry sequence that will be used to record the data entered into an electronic database system are as follows:

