To achieve Aim 1, 18 participants per group are needed to ensure significant changes in the primary mechanism of interest following both interventions relative to the control group. Between group (i.e. massage vs. control [$d=0.53$] & mobilization vs. control [$d=0.69$]) pre to post effect sizes from our preliminary data (See Preliminary Studies) were used to calculate the needed sample size. Using GPower (3.1), a repeated measures, between factors ANOVA model for three groups and two time points was used. Parameters included a purposefully conservative intra-measure correlation= 0.90 , $\alpha=0.05$, and $1-\beta=0.90$. To achieve Aim 2, 16 participants per group are needed to identify significant correlations. This value was calculated based on previously established correlations between neuromuscular mechanisms and biomechanical measures of postural control. Parameters for this analysis included a correlation of $r=0.5$ (range from literature: 0.50 to 0.58), an $\alpha=0.05$, and $1-\beta=0.90$. Thus, we will recruit 20 participants per group and plan for a 10% dropout rate, which would leave 18 subjects per group. Our previous work⁴² had a 98.75% (79/80) retention rate using the same intervention protocol and all participants completed 100% of the treatment sessions.

M.6 Stopping Rules

This study will be stopped prior to its completion if: (1) the intervention is associated with adverse effects that call into question the safety of the intervention; (2) difficulty in study recruitment or retention will significantly impact the ability to evaluate the study endpoints; (3) any new information becomes available during the trial that necessitates stopping the trial; or (4) other situations occur that might warrant stopping the trial.”

M.7 Designation of a Monitoring Committee

The Independent Monitoring Committee for this study is comprised of Drs. [name], [name], and [name]. Drs. [name], [name], and [name] are not associated with this research project and work independently of the PI, [name]. They are not part of the key personnel involved in this grant and are not affiliated with the University of North Carolina at Chapel Hill. No member of the Committee has collaborated or co-published with the PI within the past three years. They are qualified to review the patient safety data generated by this study because of their unique expertise. [name] is a PhD biostatistician. The CVs of all members of the IMC are attached.

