M.8 Safety Review Plan

Study progress and safety will be reviewed monthly (and more frequently if needed). Progress reports, including patient recruitment, retention/attrition, and AEs will be provided to the IMC semi-annually. An Annual Report will be compiled and will include a list and summary of AEs. In addition, the Annual Report will address (1) whether AE rates are consistent with pre-study assumptions; (2) reason for dropouts from the study; (3) whether all participants met entry criteria; (4) whether continuation of the study is justified on the basis that additional data are needed to accomplish the stated aims of the study; and (5) conditions whereby the study might be terminated prematurely. The Annual Report will be sent to the IMC and will be forwarded to the IRB and NCCIH. The IRB and other applicable recipients will review progress of this study on an annual basis

M.8.a Study Report Outline for the Independent Monitor(s) (Interim or Annual Reports)

The study team will generate Study Reports for the IMC and will provide information on the following study parameters: including patient recruitment, retention/attrition, and AEs. Study Report tables will be generated only from aggregate (not by group assignment) baseline and aggregate safety data for the study population.

M.8.b Submission of On-Site Monitoring/Audit and Inspection Reports

The IRB, IMC, and NCCIH Program Officials will receive copies of all study monitoring/audit or inspection reports within 14 day of PI receipt. For example, the NCCIH (Westat) monitoring report will be submitted to the IRB and IMC (NCCIH does not require copies of Westat monitoring reports). Any FDA inspection report will be submitted to the IRB, IMC, and NCCIH Program Officials.

M.8.c Table A

Data type	Frequency of review	Reviewer
Subject accrual (including compliance with protocol enrollment criteria)	Monthly	PI, Internal QA Reviewer
	Semi-annually	Independent Monitor(s)
Status of all enrolled subjects, as of date of reporting	Monthly	PI, Internal QA Reviewer
	Semi-annually	Independent Monitor(s)
Data entry quality control checks on 5% of charts	Monthly	QA Reviewer
Adherence data regarding study visits and intervention	Monthly	PI, Internal QA Reviewer
	Semi-annually	Independent Monitor(s)
AEs and rates (including out-of-range lab values)	Monthly	PI, Internal QA Reviewer
	Semi-annually	Independent Monitor(s)
	Annually	NCCIH, FDA (If Applicable)

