If a participant is determined to be ineligible for the investigation then the data collected (to determine eligibility) will be immediately destroyed. Specifically, the AII, FAAM, FAAM-S and treatment expectation data sheets will be shredded. No other data will be collected prior to determining eligibility and the potential participant reading and signing the informed consent document.

18 Plans for and Responsibilities of the Independent Monitoring Committee

An Independent Monitoring Committee (IMC) will be appointed prior to the initiation of the study in consultation with the NCCIH.

18.a Independence of the IMC

To remain objective, the IMC must maintain independence from the study. Accordingly, the IMC will not be directly or indirectly involved in the conduct of the study and does not have scientific, proprietary, financial or other interests that may affect independent decision-making.

Annually the IMC will report to the NCCIH Program Officer that no conflict of interest exists between them, the PIs or any study personnel. Such a statement may also be required prior to each review.

18.b Executive Secretary

[name] will serve as the executive secretary to facilitate the distribution of reports. All communication between the study staff and the IMC will be facilitated by [name] with NCCIH copied on the correspondence.

18.c Safety Monitoring Plan

This protocol will be continuously monitored in real-time by the principal investigator for adverse events (AEs). Participants will be discharged from the initial treatment session with specific self-monitoring guidelines (See appendix #21) and instructed to call immediately for any concerning signs or symptoms throughout the rest of the treatment period.

The full data and safety monitoring plan can be seen in Part M of the MOOP.

18.d Safety Reports

At predetermined intervals, [name] will prepare adverse event reports to be reviewed by the IMC. The adverse events are reported in aggregate by treatment groups, as requested. Serious adverse events are generally reported as they occur. The tables for reporting to the IMC are attached to this document. See Appendix 23.

18.e Roles and Responsibilities of the IMC

The IMC provides independent safety monitoring in a timely fashion to assure patient safety and study quality.

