At the beginning of the trial, the IMC will review the manual of operating procedures, containing the study protocol, study forms, and safety monitoring plan, for scope and comprehensiveness. The monitoring plan should delineate data preparation functions, the review process, and the role of the IMC. The monitoring plan also specifies the contents and format of the reports, their frequency, and triggers for ad hoc reviews. Stopping rules, if appropriate, should outline the conditions under which a study may be stopped prematurely. The IMC may suggest modifications to the protocol, the monitoring plan and the reports that will routinely be prepared by the PI.

The primary focus of the IMC's activity is participant safety. The IMC reviews adverse event reports prepared by the PI.

Serious adverse events are generally reviewed as they occur. The IMC will notify the NCCIH if a pattern of events occurs and will suggest prevention measures (e.g., modifying the protocol to require frequent measurement of laboratory values predictive of the event).

For unexpected and/or related serious adverse events, the IMC will contact the NCCIH Program representative. In addition, the IMC may request individual participant records, including objective data, subjective questionnaires, and other study related data, to evaluate these events against the known safety profile of the study treatment and the disease.

The IMC may recommend actions including modifying or terminating the study.

In addition to safety monitoring, the IMC may review enrollment data, demographic information, retention status, and other reports prepared by [name] that describe study performance and progress. The IMC will provide a report to NCCIH that describes study safety, progress and performance and provides recommendations regarding safe continuation or early termination of the trial.

The monitoring plan may require the IMC to evaluate the general performance of the study, including periodic assessment of participant recruitment, accrual and retention, protocol adherence, and data quality and timeliness. The IMC may also review any interim analyses to ensure that once the objectives of the study are met, outcome differences are detected or stopping rule thresholds are reached, the study will conclude.

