3. *Suggests that the research places subjects or others at a greater risk of harm (including physical, psychological, economic, or social harm) than was previously known or recognized.*

OHRP notes that an incident, experience, or outcome that meets the three criteria above generally will warrant consideration of substantive changes in the research protocol or informed consent process/document or other corrective actions in order to protect the safety, welfare, or rights of subjects or others.}

Adverse Events

{Summarize or list the adverse events (AEs) that have occurred since the previous IMC report and over the course of the trial. Provide information on severity and relatedness to treatment and study procedures (see an example of a summary table below). Please

ensure that categories summarized match those in the protocol. For instance related/unrelated vs. the 5 category delineation.

In addition, a summary table or listing of subjects experiencing adverse events by treatment group, system organ class, and preferred term should be considered. Extensive listings may be placed in the Appendix.

Sample Table:}

Table #. Summary of All Adverse Events for Consented Subjects

Topics	Site A	Site B	Total N=12
Number of AEs reported	38	30	68
Number of Subjects with AEs [1]	4	3	7
Number of SAEs reported	1	0	1
Number of Subjects with SAEs [1]	1	0	1
Number of AEs by Severity*	Site A	Site B	0
Mild	31 (81.1%)	24 (80.0%)	55 (80.9%)
Moderate	7 (18.9%)	3 (10.0%)	10 (14.7%)
Severe	0 (0.0%)	3 (10.0%)	3 (4.4%)
Subjects with AEs by Severity [2]**			
Mild	4 (100.0%)	3 (100.0%)	7 (58.3%)
Moderate	3 (100.0%)	2 (66.7%)	5 (41.7%)
Severe	0 (0.0%)	1 (33.3%)	1 (8.3%)
Number of AEs by Relatedness to Treatment*	Site A	Site B	Total N=12
Unrelated	25 (64.9%)	23 (76.7%)	48 (70.6%)
Unlikely	9 (24.3%)	4 (13.3%)	13 (19.1%)
Possible	4 (10.8%)	3 (10.0%)	7 (10.3%)
Probable	0 (0.0%)	0 (0.0%)	0 (0.0%)
Definite	0 (0.0%)	0 (0.0%)	0 (0.0%)
Subjects with AEs by Relatedness to Treatment [2]**	Site A	Site B	Total N=12
Unrelated	4 (100.0%)	3 (100.0%)	7 (58.3%)
Unlikely	3 (100.0%)	2 (66.7%)	5 (41.7%)
Possible	2 (66.7%)	2 (66.7%)	4 (33.3%)
Probable	0 (0.0%)	0 (0.0%)	0 (0.0%)
Definite	0 (0.0%)	0 (0.0%)	0 (0.0%)
Number of AEs by Relatedness to Study Procedures	Site A	Site B	Total N=12

Topics	Site A	Site B	Total N=12
Unrelated	26 (67.6%)	21 (70.0%)	47 (69.1%)
Unlikely	5 (13.5%)	4 (13.3%)	9 (13.2%)
Possible	4 (10.8%)	4 (13.3%)	8 (11.8%)
Probable	1 (2.7%)	1 (3.3%)	2 (2.9%)

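### M.8.a limits IMC report tables to data pooled across arms, contradicting section 18.d and the IMC report template, so routine reports under M.8.a allow no between-arm comparison of adverse events

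*Combined protocol and SAP*

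**What the plan says.** Four places bear on what the IMC sees.

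- M.8.a (report outline for interim or annual reports): "Study Report tables will be generated only from aggregate (not by group assignment) baseline and aggregate safety data".
- Appendix 1, section 18.d (Safety Reports): "The adverse events are reported in aggregate by treatment groups, as requested". It adds that the reporting tables are attached.
- IMC Report Template, Adverse Events: "a summary table or listing of subjects experiencing adverse events by treatment group, system organ class, and preferred term should be considered".
- M.2.d (Confidentiality): "AE reports and annual summaries will not include subject or group-identifiable material".

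The rules that the reports serve are these.

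- M.6, first stopping rule: the study stops if "the intervention is associated with adverse effects that call into question the safety of the intervention". No comparator, threshold or decision-maker is named.
- M.2.k, halting rules: "Safety findings including, but not limited to, higher than anticipated SAEs, a higher number of a particular SAE than anticipated", together with increased AE frequency. No number is given.
- M.8: the Annual Report addresses "whether AE rates are consistent with pre-study assumptions".
- Appendix 1, section 18.e: "The IMC may recommend actions including modifying or terminating the study".

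**The concern.** The trial has two therapy arms and an untreated control arm, and all three undergo TMS and EEG at each test session. By the rates in M.2.e, most expected events come from that testing, so they occur in every arm. The control arm could serve as a background against which events in the therapy arms are judged, but only if someone independent sees events by arm. M.8.a withholds that from the IMC's routine tables, while 18.d and the template allow for it.

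The condition in 18.d that the IMC must ask does not remove the conflict. If the IMC asks, 18.d says the tables are supplied, and the word only in M.8.a says they are not. At stake is whether the IMC has a check on ordinary AEs that does not depend on the study team's judgement of each event.

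**Working it through.** The plan states no figure to reproduce: the first stopping rule has no threshold and the monitoring plan no operating characteristics. The check is a comparison of texts, followed by illustrations with assumed event splits.

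**1. The texts side by side**

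| Place | By-arm AE data to the IMC? |
|---|---|
| M.8.a | No; tables only from pooled data |
| Appendix 1, 18.d | Yes, when requested |
| IMC Report Template | To be considered (generic guidance) |
| M.2.d | Unclear; group may mean treatment arm or an identifiable group of people |

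The first row contradicts the second and departs from the third. The fourth cannot be settled from its wording.

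**2. Inputs**

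- 20 per arm, 60 in total (M.5).
- EEG scalp itching 10%, TMS effects 5%, manual-therapy discomfort below 1% (M.2.e). I read these as per participant, which is an assumption. Three test sessions with per-session rates would raise the background.

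**3. Same pooled count, different splits (splits assumed)**

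The EEG rate alone gives 60 × 0.10 = 6 participants. A pooled 6/60 is compatible with both of these:

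- 2/2/2: no difference between arms;
- 6/0/0: 6/20 against 0/20, two-sided Fisher exact p = 0.020.

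The pooled count is the same in both.

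**4. How far harm in one arm moves the pooled count**

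With background rate b in two arms and rate t in the third, the expected pooled count is 40b + 20t, against 60b with no excess.

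| b (assumed) | No excess | t = 20% | t = 30% | t = 40% |
|---|---|---|---|---|
| 5% | 3 | 6 | 8 | 10 |
| 10% | 6 | 8 | 10 | 12 |
| 15% | 9 | 10 | 12 | 14 |

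At b = 10%, the pooled rates are 13.3%, 16.7% and 20.0%. An exact one-sided pooled test against a known 10% rejects at 11 or more of 60 (actual level 0.034). Its power is 17%, 42% and 69% for t = 20%, 30% and 40%.

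A two-sided 5% Fisher test of 20 against 20 has power of only 7%, 24% and 49% in the same cases. The by-arm table is therefore not a more powerful formal test. The pooled test does better only because it is one-sided and takes the background as known exactly. If the true background were 13.3%, the pooled expectation would be 60 × 0.133 = 8, the same as a 10% background with one arm at 20%. Pooled data can show an overall excess if the background is known, but cannot place it in an arm.

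**5. What a pooled table can still show**

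Pooled across arms does not mean pooled across event types. Expected therapy discomfort is at most 40 × 0.01 = 0.4. The Poisson probability of three or more is 1 − e^(−0.4)(1 + 0.4 + 0.08) = 0.008. Three such events would stand out in a pooled table by type. The gap concerns event types that testing also produces, and events whose cause is uncertain.

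**The case against.** The strongest reply is that the IMC has other routes. The AE form codes each event's relationship to the intervention on five levels. Table A in M.8.c gives the monitors per-occurrence notice of unexpected and related SAEs. Section 18.e lets the IMC request individual records for unexpected and/or related SAEs. The template's sample table separates relatedness to treatment from relatedness to study procedures without showing arms. Controls receive no therapy, so an event during a treatment session must come from a therapy arm. The halting rules and the Annual Report both work from anticipated rates, which pooled data can serve.

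Most of this stands, and it limits the point. It does not close the gap. The notice and records routes concern SAEs, not ordinary AEs. The AE form in Appendix 10 has no field for relatedness to study procedures. The relatedness code is a judgement made event by event within the study team, whose PI records the assignments.

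A reader might infer four stronger things that the documents do not support:

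- That the IMC is unable to use the first stopping rule. The rule requires no comparison of arms, and M.6 does not assign it to the IMC, which may recommend termination.
- That M.2.d also forbids by-arm data. It is a confidentiality clause, and its next sentence concerns identification codes.
- That 18.d guarantees by-arm tables. It depends on a request.
- That the IMC is the sole outside check. Unanticipated problems and the Annual Report also go to the IRB and NCCIH.

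**Conclusion.** The point holds as a contradiction with a limited consequence. M.8.a and 18.d cannot both be followed once the IMC asks for by-arm data, and M.8.a also departs from the template. Under M.8.a, the routine reports allow no between-arm comparison of AEs. That weakens assessment of whether the intervention is associated with harm, chiefly for event types that TMS and EEG also produce. It does not disable the assessment: event-type tables, relatedness coding and the SAE routes remain.

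The contradiction rests on the text alone. The illustrations rest on assumed splits and on reading the M.2.e rates as per participant; they show that arms cannot be told apart from a pooled count, not how likely harm is. The correction should be made, but the conflict does not undermine the design.

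**What to change.** - Amend M.8.a to agree with 18.d. The open report stays pooled. The IMC also receives a closed table of AEs and SAEs by coded arm (A/B/C), and by relatedness to treatment and to study procedures as in the template's sample table. No efficacy data are included.
- Have it prepared by the study biostatistician, who already generates the randomization list, or by another person who does not assess outcomes, so that assessor blinding is kept.
- State in M.2.d whether its reference to groups means treatment arm.
- If relatedness to study procedures is to be tabulated, add that field to the AE form in Appendix 10.

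The cost is one extra table per report and possibly one form field. Design, sample size and treatment do not change. A lighter alternative keeps pooled tables as the default and writes the on-request route into M.8.a as an explicit exception. That removes the contradiction, but gives the IMC an arm comparison only when it thinks to ask.
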